1 PROTOCOL SYNOPSIS

Trial Title	An exploratory, Phase 2, randomized, double-blind, placebo-controlled trial to investigate the safety and efficacy of cannabidiol oral solution (GWP42003-P; CBD-OS) in children and adolescents with Autism Spectrum Disorder		
Clinical Trial Type	Phase 2		
Indication	Autism Spectrum Disorder		
Objectives and	Efficacy Objective	Efficacy Endpoints	
Linupoliits	• To evaluate the efficacy of GWP42003-P, compared with placebo, in reducing symptom severity in children with ASD.	 Behavior ABC Subscales Social Communication VABS-3 Overall Condition CGI-I CGI-S 	
	Safety Objective	Safety Endpoints	
	• To evaluate the safety of GWP42003-P, compared with placebo, in children with ASD.	 AEs. Clinical laboratory parameters. Vital signs. Physical examination procedures. 12-lead ECG. C-SSRS. 	

Trial Design	This is an exploratory, Phase 2, double-blind, randomized, placebo-controlled, multisite trial, which will compare the safety and efficacy of a 10 mg/kg/day dose of GWP42003-P versus placebo in children and adolescents with ASD. Patients will be screened and if they meet eligibility criteria, they will be		
	randomized to receive GWP42003-P or matching placebo in a 1:1 ratio. Patients will be stratified based on their age (6 to 11, 12 to 17), use of antipsychotics (on versus off), and region (North America versus Rest of the World). Patients will be administered 5 mg/kg/day GWP42003-P or matching volumes of placebo for 1 week and then 10 mg/kg/day GWP42003-P or matching volumes of placebo for 11 weeks. At the end of treatment, patients will taper the medication over 1 week.		
	In order to facilitate trial execution in the context of infectious diseases or other transmissible conditions (e.g., COVID-19), the trial will involve a combination of clinic, remote (including a video call and a home nurse visit) and telephone visits, as specified in APPENDIX 1.		
Sample Size	160 patients randomized to allow for 144 evaluable patients (72 evaluable patients per arm) at trial end.		
Summary of	Inclusion Criteria		
Patient Eligibility	For inclusion in the trial, patients must fulfill ALL of the following criteria:		
Criteria	• Male or female aged 6 to 17 years (inclusive).		
	• Patient weight is at least 12 kg.		
	• Patients (if possessing adequate understanding, in the investigator's opinion) and their parent(s)/legal representative are willing and able to give informed assent and consent for participation in the trial.		
	• Patient and their caregiver are willing and able (in the investigator's opinion) to comply with all trial requirements.		
	• Patient has a diagnosis of ASD as per DSM-5 criteria for ASD, confirmed by ADOS-2 criteria (conducted within 2 years at the trial site or at screening by a qualified assessor). Note: During special circumstances (e.g., COVID-19 pandemic) where the ADOS-2 cannot be performed due to site restrictions (e.g., mandatory use of face masks) and an ADOS-2 conducted within 2 years at the trial site by a qualified assessor is not available, eligibility can be confirmed using: 1) an ADOS-2 performed within 2 years by a qualified assessor		

	(external to the site); 2) if 1) is not available, eligibility may be confirmed using the ADI-R at screening.
•	CGI-S \geq 4 (moderately ill) at screening and randomization.
•	ABC-I subscale score ≥ 15 at screening.
•	IQ \geq 70 at screening, or measured within 1 year of screening, using WASI-II.
•	All medications or interventions (including psychosocial interventions, dietary supplements, probiotics, speech therapy, etc.) for ASD related symptoms must have been stable for 4 weeks prior to screening and randomization, and the patient/caregiver should be willing to maintain a stable regimen throughout the trial.
•	Patients must have the ability to swallow the IMP, provided as a liquid solution.
•	Patient and/or parent(s)/legal representative is willing to allow the responsible authorities to be notified of participation in the trial, if mandated by local law.
•	Patient and/or parent(s)/legal representative is/are willing to allow the patient's primary care practitioner (if they have one) and consultant (if they have one) to be notified of participation in the trial if the primary care practitioner/consultant is different from the investigator.
Exc	lusion Criteria
The	e patient may not enter the trial if ANY of the following apply:
•	Current diagnosis of bipolar disorder, psychosis, schizophrenia, schizoaffective disorder, or major depression (patients with depression in remission may be included).
•	Has a diagnosis other than ASD that dominates the clinical presentation (e.g., ADHD).
•	Has a progressive neurological condition.
•	Seizures in the past 24 weeks.
•	Changes in anticonvulsive therapy within the last 12 weeks.
•	Currently taking more than 2 AEDs.
•	Taking sirolimus, everolimus, temsirolimus, or tacrolimus.
•	Taking clobazam.
•	Taking omeprazole, lansoprazole, tolbutamide, or warfarin.
•	Taking repaglinide, pioglitazone, rosiglitazone, montelukast, bupropion, or efavirenz.
•	Currently using or has used recreational or medicinal cannabis,
	cannabinoid-based medications (including Sativex [®] , or
	Epidiolex [®] /Epidyolex [®]) within the 12 weeks prior to screening and is unwilling to abstain for the duration of the trial.

• Patient has any known or suspected hypersensitivity to cannabinoids or any of the excipients of the IMP, such as sesame oil.
• Patient has moderately impaired hepatic function at screening, defined as serum ALT or AST > 2 × ULN or TBL > 2 × ULN'
This criterion can only be confirmed once the laboratory results are available; patients enrolled into the trial who are later found to meet this criterion must be screen-failed.
• Patient is male and fertile (i.e., after puberty unless permanently sterile by bilateral orchidectomy) unless willing to ensure that they use male contraception (condom) or remain sexually abstinent during the trial and for 12 weeks thereafter.
• Patient is female and of childbearing potential (i.e., following menarche and until becoming postmenopausal for ≥ 12 consecutive months unless permanently sterile by hysterectomy, bilateral salpingectomy, or bilateral oophorectomy) unless willing to ensure that they use a highly effective method of birth control (e.g., hormonal contraception, intrauterine device/hormone-releasing system, bilateral tubal occlusion, vasectomized partner, sexual abstinence) during the trial and for 12 weeks thereafter.
• Female patient who is pregnant (positive pregnancy test), lactating or planning pregnancy during the course of the trial or within 12 weeks thereafter.
• Patient has received an IMP within the 12 weeks prior to the screening visit.
• Patient had brain surgery or traumatic brain injury within 1 year of screening.
• Patient has any other significant disease or disorder which, in the opinion of the investigator, may either put the patient, other participants, or site staff at risk because of participation in the trial, may influence the result of the trial, or may affect the patient's ability to take part in the trial.
• Any abnormalities identified following a physical examination of the patient that, in the opinion of the investigator, would jeopardize the safety of the patient if they took part in the trial.
• Any history of suicidal behavior (lifelong) or any suicidal ideation of type 4 or 5 on the C-SSRS in the last 4 weeks or at screening or randomization.
• Patient has donated blood during the past 12 weeks and is unwilling to abstain from donation of blood during the trial.
• Patient has any known or suspected history of alcohol or substance abuse or positive drugs of abuse test at screening (not justified by a known concurrent medication).

	• Patient has previously been randomized into this trial.
	• Patient has plans to travel outside their country of residence during the trial, unless the patient has confirmation that the IMP is permitted in the destination country/state.
Criteria for	The patient must be withdrawn from the trial if any of the following apply:
Withdrawal	• Administrative decision by the investigator, GW or regulatory authority.
	• Did not meet eligibility criteria.
	• Pregnancy.
	 Protocol deviation that is considered to potentially compromise the safety of the patient.
	• Withdrawal of patient consent/assent.
	• Withdrawal of parent(s)/legal representative consent.
	• ALT or AST > 3 × ULN with the appearance of fatigue, nausea, vomiting, right upper quadrant pain or tenderness, fever, rash, and/or eosinophilia (> 5%).
	• ALT or AST $> 8 \times$ ULN.
	• ALT or $AST > 5 \times ULN$ for more than 2 weeks.
	• ALT or AST > $3 \times$ ULN and (TBL > $2 \times$ ULN or INR > 1.5).
	• Note: Prior to treatment discontinuation for the transaminase elevations noted above, the investigator may choose to confirm the transaminase elevations by repeating the following laboratory tests, tests within 24 to 48 hours: ALT, AST, TBL, INR, % eosinophils, gamma- glutamyl transferase and alkaline phosphatase. Should the above transaminase elevation criteria be confirmed, the patient must be withdrawn from the trial. In cases where transaminase elevation
	withdrawal criteria are not met or confirmed, the dose of IMP or a
	concomitant medication with known hepatotoxicity may be reduced
	following discussion with the medical monitor.
	• Lost to follow-up.
	The patient may also be withdrawn from the trial for any of the following:
	• Patient noncompliance.
	• AE (including clinically significant laboratory result) which, in the opinion of the investigator, would compromise the continued safe participation of the patient in the trial.
	• Patient cannot tolerate a dose level of 5 mg/kg/day.
	• Any evidence of use of drugs of abuse or drug diversion.
	• Suicidal ideation or behavior of type 4 or 5 during the treatment period, as evaluated with the C-SSRS.

Investigational Medicinal Product: Formulation, Mode of Administration, Dose and Regimen	GWP42003-P oral solution (100 mg/mL CBD in sesame oil with anhydrous ethanol, ethanol (10% v/v) sweetener [sucralose], and strawberry flavoring). Mode of administration: to be taken orally b.i.d. (morning and evening) using the syringe(s) provided, preferentially with food i.e., within 30 minutes after the end of a meal/snack. The time of IMP administration in relation to food should be kept consistent throughout the trial. Volume of IMP to be determined by patient's weight.
Control Group	Placebo to match GWP42003-P oral solution containing sesame oil with anhydrous ethanol, sweetener (sucralose), strawberry flavoring, and beta carotene.
Procedures	 Before undergoing any assessments or observations, the patient's parent(s)/legal representative is required to give written informed consent. In cases where the patient possesses adequate understanding, their assent will be taken, along with parental/legal representative consent. Screening (Visit 1) assessments/procedures will include: Informed consent/assent; eligibility criteria checks; demographics; medical history. Concomitant medications/therapies; AE/SAE review. Test for drugs of abuse. Full physical examinations; including height, weight, and BMI. 12-lead ECG. Hematology; biochemistry (including liver chemistries); and urinalysis. Serum pregnancy test (WOCBP only). C-SSRS. Vital signs. WASI-II (if required), ADOS-2 (if required, or ADI-R under special circumstances). ABC, CGI-S. Treatment Period (Visits 2 to 8) assessments/procedures will include (please refer to APPENDIX 1 for frequency of assessments): Randomization Concomitant medications/therapies; AE/SAE review
	 Hematology and biochemistry (including liver chemistries) C-SSRS

	 ABC, Vineland-3, CGI-S, CGI-I, IMP dispensing IMP review Note: Visits 3, 4, 6, and 10 are to be conducted by telephone End of Taper (Visit 9) assessments/procedures will include: Concomitant medications/therapies; AE/SAE review C-SSRS Vital signs Hematology; biochemistry (including liver chemistries); and urinalysis Serum pregnancy test (WOCBP only) IMP review Follow-up (Visit 10) assessments/procedures will include: Concomitant medications/therapies; AE/SAE review Additional procedures to screen for the presence of or immunity against infectious diseases (such as body temperature, sampling of nasal mucosal cells, or serology) may be conducted at screening, at the beginning of each visit, or as needed, according to local guidance and policy.
Statistical Considerations	All safety and efficacy data will be summarized and analyzed using appropriate statistical methods. Questionnaires will be summarized at each visit along with the change from baseline, where appropriate. As this is an exploratory trial, there will be no type I error adjustments with all hypothesis testing performed at a 5% significance level.
Safety Monitoring Committee	Not applicable.
Sponsor	GW Research Ltd [name]

Study Code: GWND19189 IND Number: 150775 Protocol Version 2.0, 24 Nov 2020 Figure 1-1 Trial Design and Treatment Schematic

Page 10 of 88

Confidential Clinical Protocol Template (Phase 2–4)

Table of Contents

Title	Page	1
1	PROTOCOL SYNOPSIS	
Tabl	e of Contents	11
List	of Appendices	
List	of In-text Tables	
List	of In-text Figures	
List	of Abbreviations	17
Defi	nition of Terms	20
2	OBJECTIVES AND ENDPOINTS	21
3	BACKGROUND AND RATIONALE	
3.1	Disease	
3.2	Cannabidiol Background	
3.3	Rationale	
3.3.1	Choice of Efficacy and Exploratory Endpoints	
3.3.2	Choice of Dosing Regimen	
3.3.3	Benefit-Risk	
3.4	Clinical Hypothesis	
4	EXPERIMENTAL PLAN	
4.1	Trial Design	
4.2	Number of Centers	
4.3	Number of Patients	
5	INVESTIGATIONAL MEDICINAL PRODUCT	
5.1	GWP42003-P Oral Solution	
5.2	Placebo	
5.3	Packaging, Storage and Drug Accountability	
5.3.1	Packaging and Labeling	
5.3.2	Storage	
5.3.3	Supply and Return of Investigational Medicinal Product	
5.3.4	Investigational Medicinal Product Accountability	

5.3.5	Post-Trial Provision	5
6	PATIENT ELIGIBILITY	6
6.1	Inclusion Criteria	6
6.2	Exclusion Criteria	6
7	PATIENT ENROLLMENT	9
7.1	Treatment Assignment	9
8	TREATMENT PROCEDURES	0

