In general, the key risks identified from the clinical development program for LGS and DS are broadly expected to be the same for the ASD population – as the patient demographics and comorbidities have a significant amount of overlap. It is important to note that several of the key

risks for CBD-OS are dose related, as such the lower doses planned for the current trial may improve the tolerability of CBD-OS:

Hepatocellular injury is anticipated to be an important risk for CBD-OS in ASD patients, although to date the transaminase elevations observed with CBD-OS treatment have generally been asymptomatic, with no Hy's law cases reported from any source. The proposed dose level of 10 mg/kg/day may provide an improved tolerability compared to the 10 and 20 mg/kg/day doses employed in the LGS and DS program. Furthermore, the transaminase elevations in LGS and DS patients were markedly more frequent and of a greater magnitude in patients taking concomitant VPA. Of note, VPA use is expected to be less frequent in the ASD population than in the LGS and DS populations, providing an additional avenue to an improved tolerability to CBD-OS with respect to potential hepatocellular injury.

Somnolence type events are anticipated to be important risks for CBD-OS in ASD patients; however, from experience in LGS and DS patients, such events were manageable, and only a minority needed to discontinue CBD-OS. Dose adjustment should help mitigate any events of somnolence and sedation if needed. The somnolence may also diminish with repeated dosing over time.

Cannabidiol oral solution has been shown to cause loss of weight in clinical trials, however the incidence of a significant loss of weight (> 5%) was noted to be similar between the CBD-OS dose of 10 mg/kg/day and placebo in placebo-controlled trials. There was no impact on growth, as measured through BMI or height in these trials.

In DS/LGS studies, aggression was reported in 2.2% of patients in the 10 mg/kg/day group while irritability was reported in 7.2% of patients in the 10 mg/kg/day group. The majority of cases reported were of mild or moderate severity with only few cases leading to withdrawal from these trials.

A higher incidence of pneumonia was noted with CBD-OS in LGS and DS controlled trials, although incidence does not appear to be dose related, majority of patients has risk factors for pneumonia and no plausible mechanism has been identified.

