8.3 Clinical Laboratory Results

Laboratory tests will include hematology, serum biochemistry, coagulation (Visit 1 only; thereafter only as an unscheduled assessment if ALT or AST > 3 x ULN), Clinical laboratory sample parameters are detailed in Table 9.1-1 in the study protocol. Urinary data and the drug abuse data will only be listed.

In case of values <LLoQ or >ULoQ, LLoQ or ULoQ, respectively, will be used in summary tables.

All test results and abnormal laboratory values will be presented in data listings.

Summaries of actual values and changes from baseline for numeric test results will be presented for each assessment time point.

Shift tables will be summarizing the counts and percentages of subject's baseline CTCAE grade versus worst CTCAE grade at any postbaseline visit.

Potential Cases of Drug-Induced Liver Injury

A table will summarize the number of subjects by the following criteria.

At baseline:

- ALT > 1 x ULN
- AST > 1 x ULN
- ALT or AST > 1 x ULN
- TBIL > 1 x ULN
- ALT or AST or TBIL > 1 x ULN

At any time point after first dose of study treatment:

- ALT > N x ULN, where N=1, 2, 3, 5, 8
- AST > N x ULN, where N=1, 2, 3, 5, 8
- ALT or AST > N x ULN, where N=1, 2, 3, 5, 8
- ALP > 2 x ULN
- TBIL > 1 x ULN
- TBIL > 2 x ULN
- ALT or AST > 3 x ULN and TBIL > 2 x ULN
- ALT or AST>3 x ULN and INR > 1.5

The summary table will be done by sex,

and

overall.

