8.4 Vital Signs

Vital signs include body temperature, pulse rate, respiratory rate and blood pressure taken in a sitting position at rest for 5 minutes, and are measured at Visit 1 (Screening), Visit 2, Visit 5, Visit 8 EoT/WD, and Visit 9.

Summary of actual values and changes from baseline will be presented for each assessment time point.

The number and percentage of subjects with marked abnormalities post-baseline will be tabulated for each vital sign marked abnormality category. In the listings, the marked abnormalities are classified as high (H, HH) or low (L, LL) based on values occurring above the higher limit or below the lower limit, respectively. Only the most severe abnormality will be counted (e.g. a subject meeting the 'HH' criterion for a specific parameter will not be summarized under 'H' for this parameter. Percentages will be based on the number of subjects at risk for the parameter: those not meeting the criterion at baseline (or having a missing baseline value) and having at least one post-baseline value. The vital signs marked abnormality categories are presented in the table below.

Table 4 Marked abnormalities for vital signs

Parameter (unit)	Abnormality
Weight (kg)	Decrease from baseline > 7% (L flag)
	Increase from baseline > 7% (H flag)
Body temperature (C)	< 36 (L flag)
	> 38 (H flag)
Pulse rate (beats/min)	< 60 (L flag)
	> 100 (H flag)
Respiratory rate (breaths/min)	< 12 (L flag)
	> 20 (H flag)
Systolic blood pressure (mmHg)	< 90 (L flag)
	> 140 (H flag)
	> 160 (HH flag)
Diastolic blood pressure (mmHg)	< 50 (L flag)
	> 90 (H flag)
	> 100 (HH flag)

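### SAP 8.3 liver table: the > 1 x ULN rows (ALT, AST, ALT or AST, TBIL) and the ALP > 2 x ULN row mix elevations present before dosing with new ones

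*Protocol*

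**What the plan says.** **Entry.** The Protocol Synopsis and Section 6.2.13 exclude a child on this ground: "Patient has moderately impaired hepatic function at screening, defined as serum ALT or AST > 2 × ULN or TBL > 2 × ULN". The Synopsis adds that "patients enrolled into the trial who are later found to meet this criterion must be screen-failed". Values above 1 x and up to 2 x ULN are therefore admitted. No exclusion criterion names ALP.

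**Liver table.** SAP 8.3 has a block headed "At any time point after first dose of study treatment". Its rows include "ALT or AST > N x ULN, where N=1, 2, 3, 5, 8", the same multiples for ALT and AST separately, TBIL above 1 x and 2 x ULN, and ALP above 2 x ULN. No row carries a condition on the baseline value. A separate baseline block counts ALT, AST, either of them, and TBIL above 1 x ULN, and ends with "ALT or AST or TBIL > 1 x ULN". It has no ALP row.

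**Other laboratory outputs.** SAP 8.3 also plans change-from-baseline summaries, listings, and shift tables of "counts and percentages of subject's baseline CTCAE grade versus worst CTCAE grade at any postbaseline visit". Protocol 13.6.3.3 plans categorical shift tables for values outside the normal range.

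**A rule used elsewhere.** For marked vital-sign abnormalities, SAP 8.4 states: "Percentages will be based on the number of subjects at risk for the parameter: those not meeting the criterion at baseline". Subjects with a missing baseline also count as at risk, and at least one post-baseline value is required. SAP 8.6 takes a similar approach for ECG.

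**Importance of the risk.** Protocol 3.2 says: "Hepatocellular injury is anticipated to be an important risk for CBD-OS in ASD patients".

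**The concern.** A child who enters at 1.5 x ULN and stays there is counted after dosing in the > 1 x ULN row, exactly like a child who was normal and became elevated. The same can happen with ALP above 2 x ULN, where the table does not show even a baseline count.

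Two things follow. In expectation, randomization adds the same background to both arms, which pulls the ratio between arms towards 1. By chance, the background can also differ between arms, because randomization is stratified on age, antipsychotic use and region but not on liver values. The low-multiple rows are where a mild hepatic effect would show. The SAP already has a rule that removes this background for vital signs, but does not apply it here.

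**Working it through.** **1. Which rows can hold a pre-existing elevation?** Set the entry limits against the table limits. Baseline is the last observation before the first dose (SAP 4.2). The only scheduled pre-dose safety laboratory sample is Visit 1 (Protocol Appendix 1).

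| Row | Entry limit | Can a correctly enrolled child already meet it? |
|---|---|---|
| ALT, AST, ALT or AST, TBIL > 1 x ULN | 2 x ULN | Yes |
| ALP > 2 x ULN | none | Yes |
| ALT, AST, ALT or AST, TBIL > 2 x ULN | 2 x ULN | No, barring an entry violation or an unscheduled pre-dose retest |
| ALT, AST > 3 x, 5 x, 8 x ULN; combined rows | 2 x ULN | No, with the same exceptions |

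**2. Size if every baseline elevation persists.** The plan states no figure to reproduce, so all rates here are assumptions. Let p be the share above 1 x ULN at baseline and r the rate of new elevation among the rest. The table then shows p + (1 - p) x r. Take r = 10% on drug and 3% on placebo, a true difference of 7.0 points and a true ratio of 3.33.

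| p (children per arm of 80) | Drug | Placebo | Difference | Ratio |
|---|---|---|---|---|
| 5% (4) | 0.05 + 0.95 x 0.10 = 14.5% | 0.05 + 0.95 x 0.03 = 7.85% | 6.65 points | 1.85 |
| 10% (8) | 0.10 + 0.90 x 0.10 = 19.0% | 0.10 + 0.90 x 0.03 = 12.7% | 6.30 points | 1.50 |
| 15% (12) | 0.15 + 0.85 x 0.10 = 23.5% | 0.15 + 0.85 x 0.03 = 17.55% | 5.95 points | 1.34 |

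The difference falls by 0.35 to 1.05 points, and the ratio falls much more.

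**3. Size if only some persist.** Let s be the chance that a child elevated at baseline is elevated again after dosing. The row shows p x s + (1 - p) x r when s exceeds r. With other assumed rates (15% on drug, 5% on placebo, true ratio 3.0), p from 2% to 15% and s from 0.5 to 1.0:

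- the ratio lies between 2.7 (p = 2%, s = 0.5) and 1.4 (p = 15%, s = 1.0);
- the difference is (1 - p) x 10 points, that is 9.8 to 8.5 points.

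**4. Chance imbalance.** The SD of the between-arm difference in baseline prevalence is the square root of 2p(1 - p)/80. For p = 5% this is the square root of 0.0011875, or 3.4 points. For p = 15% it is the square root of 0.0031875, or 5.6 points. With full persistence, a one-point baseline imbalance moves the post-dose row by 1 - r points, that is 0.90 (drug) to 0.97 (placebo). An imbalance of one SD therefore moves the post-dose difference by about 3.1 (3.4 x 0.90) to 5.4 (5.6 x 0.97) points, against the assumed true 7.0 in step 2. This exceeds the dilution.

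**5. With an at-risk denominator.** Children above the limit at baseline leave both numerator and denominator. The row then shows r in each arm: 10% against 3% in step 2, and 15% against 5% in step 3.

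**The case against.** **The baseline rows let a reader subtract.** If every elevation persists, they do: 14.5% - 5% = 9.5%, and 9.5/95 = 10%, the assumed new rate. With partial persistence they do not. On placebo with p = 10%, s = 0.5 and r = 5%, the row shows 0.10 x 0.5 + 0.90 x 0.05 = 9.5%. Subtracting the 10% baseline count gives -0.5%, when new cases are 4.5% of the arm. Marginal counts reveal a baseline imbalance but do not identify new cases. For ALP there is nothing to subtract.

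**Shift tables cover it.** They do in part. A normal-range shift table as in Protocol 13.6.3.3 would separate new from existing elevations above 1 x ULN for a single analyte. SAP 8.3, however, specifies its shift tables by CTCAE grade, and the documents do not give the grade limits. Neither form gives the ALT-or-AST composite or is tied to these multiples.

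**The absolute difference hardly moves, and the plan specifies no ratio or test for this table.** This stands, and it is why the point is minor.

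**The denominator may be set in the table specifications.** These are in a separate document, so that is possible. But the SAP text states the at-risk rule for vital signs and not for liver values, so a programmer following it would not apply the rule here.

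**The table is about potential drug-induced liver injury, for which Protocol 12.8 starts at > 3 x ULN.** This stands for those rows. Peak levels beside baseline counts are also a legitimate display, so the rows are incomplete rather than wrong.

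**A stronger reading concerns the > 2 x ULN rows.** A reader might infer that they are contaminated too, because a child entering at 1.9 x ULN can cross 2 x on ordinary variation. The documents do not support this for ALT, AST or TBIL. That child did not meet the criterion at baseline, so the crossing is new, and an at-risk rule would still count it.

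**Conclusion.** The point holds for the > 1 x ULN rows of ALT, AST, ALT or AST, and TBIL, and for ALP > 2 x ULN. These rows combine elevations that preceded treatment with those that followed it, and no planned output fully separates the two at these limits.

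The size is modest. Under the rates assumed in step 2 with full persistence, the difference between arms shrinks by about 0.4 to 1 point and the ratio falls from 3.33 to between 1.85 and 1.34. With lower persistence the ratio is diluted less. The larger benefit of a change is to take chance baseline imbalance out of these rows. Baseline prevalence, persistence and new-onset rates are all assumptions. For ALP, the documents show only that mixing is possible, not how often.

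A reader might go further and infer that the plan cannot detect serious liver injury, or that the entry limit is at fault. Neither follows. The 3 x and higher rows and the combined rows are unaffected, and the point concerns only how a table is counted. It is a cheap, minor improvement.

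**What to change.** In SAP 8.3, for the > 1 x ULN rows (ALT, AST, ALT or AST, TBIL) and the ALP > 2 x ULN row only, state that counts and percentages use subjects at risk as in SAP 8.4: criterion not met at baseline, or baseline missing, with at least one post-dose value. For the composite row, at risk means that neither ALT nor AST was above 1 x ULN at baseline.

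Add a cross-tabulation of baseline multiple (up to 1 x; above 1 x to 2 x ULN) by worst post-dose multiple, so that children elevated at baseline stay visible. ALP has no entry limit, so it also needs a baseline category above 2 x ULN.

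Leave the ALT, AST and TBIL > 2 x rows, the 3 x, 5 x and 8 x rows and the combined rows as they are.

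The cost is one or two sentences in the SAP, a changed denominator in a few rows and one small table. No new data and no protocol amendment are needed. The downside is that denominators will differ slightly between rows, so each row should print its own.
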